- 13. Investigator site staff directly involved in the conduct of the study and their family members, site staff otherwise supervised by the investigator, and sponsor and sponsor delegate employees directly involved in the conduct of the study and their family members.

Study Arms and Duration: The total duration of participation from the screening visit to the telephone follow-up contact will be approximately 15 weeks for each participant.

Study Intervention(s)										
Intervention Name	PF-06954522	Placebo								
Use	Experimental	Placebo								
IMP or NIMP/AxMP	IMP	IMP								
Dose Formulation	Bulk powder for extemporaneous preparation of oral suspensions	Bulk powder for extemporaneous preparation of oral suspensions								
Unit Dose Strength(s)	CCI mg	0 mg								
Route of Administration	Oral	Oral								

Study Arm(s)												
Arm Title	Cohort 1	Cohort 2 (Optional)	Cohort 3 (Optional)									
Arm Description	Participants may receive up to 5 dose levels of PF-06954522 and matching placebo. Doses will be administered as oral suspensions as escalating single doses to be determined.	Participants may receive up to 4 dose levels of PF-06954522 and matching placebo. Doses will be administered as oral suspensions as escalating single doses to be determined.	Participants may receive up to 3 dose levels of PF-06954522 and matching placebo. Doses will be administered as oral suspensions as escalating single doses to be determined.									

Assessment of the safety, tolerability, and PK after each single dose level will be conducted before escalating to the next dose level. The dose/exposure-escalation increments are planned to be up to approximate semi-logarithmic increases in exposure from the previous highest dose level that has been evaluated. The actual dose levels, target exposures, and/or dose level increments may be adjusted during the study based on emerging human safety, tolerability, and PK data, but projected exposures will not exceed the predefined human exposure limits.

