Participants will be screened within 28 days of their first dose of study intervention (Period 1, Day 1). Participants will be admitted to the CRU on Day -1 of each study period and will remain in the CRU through at least the 72-hour assessments on Day 4. Participants may remain in the CRU after completion of Day 4 activities at the discretion of the investigator or if safety, tolerability, or PK data dictate the need to prolong confinement in the CRU. Participants will receive a single oral dose of PF-06954522 or placebo on Day 1 of each period.

Between each dose administration to a given participant there will be a washout interval of at least 7 days. The washout interval may be increased based on data emerging from previous cohorts/periods. Dose escalation will occur only after the previous dose level was demonstrated to be well tolerated with an acceptable safety profile based on review of the emerging safety and PK data (see Section 6.6.1). Dose levels will be escalated to bracket the expected clinical dose range, but the projected exposures will not exceed the predefined human exposure limits. An on-site follow-up visit and a telephone follow-up contact will take place 7-10 days and 28-35 days, respectively, after the last dose of study intervention in the final period, or after early discontinuation. At the discretion of the investigator, telephone follow-up contact may be substituted with an on-site visit in case of additional follow-up of open AEs or clinically significant laboratory findings. Therefore, the total planned duration of participation, from the Screening visit to the follow-up phone call, will be approximately 13 weeks for Cohort 1, 12 weeks for optional Cohort 2 and 11 weeks for optional Cohort 3 (if performed as a 3-way crossover).

Dosing of study intervention is anticipated to occur following a fast of at least 10 hours. Dose administration may also occur in the fed state (following a high-fat breakfast, see Section 5.3.2), in order to explore any potential food effect on PF-06954522 PK. If this assessment is conducted, it is anticipated that the study intervention will be administered in

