8.4.1. Time Period and Frequency for Collecting AE and SAE Information

The time period for actively eliciting and collecting AEs and SAEs ("active collection period") for each participant begins from the time the participant provides informed consent, which is obtained before undergoing any study-related procedure and/or receiving study intervention), through and including a minimum of 28 calendar days, except as indicated below, after the last administration of the study intervention.

Follow-up by the investigator continues throughout the active collection period and until the AE or SAE or its sequelae resolve or stabilize at a level acceptable to the investigator.

When a clinically important AE remains ongoing at the end of the active collection period, follow-up by the investigator continues until the AE or SAE or its sequelae resolve or stabilize at a level acceptable to the investigator and Pfizer concurs with that assessment.

For participants who are screen failures, the active collection period ends when screen failure status is determined.

If the participant withdraws from the study and also withdraws consent for the collection of future information, the active collection period ends when consent is withdrawn.

If a participant permanently discontinues or temporarily discontinues study intervention because of an AE or SAE, the AE or SAE must be recorded on the CRF and the SAE reported using the CT SAE Report Form.

Investigators are not obligated to actively seek information on AEs or SAEs after the participant has concluded study participation. However, if the investigator learns of any SAE, including a death, at any time after a participant has concluded study participation, and they consider the event to be reasonably related to the study intervention, the investigator must promptly report the SAE to Pfizer using the CT SAE Report Form.

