- Each period will consist of admission on Day -1, dosing on Day 1, and discharge on Day 4. There will be a washout interval of at least 7 days between consecutive doses administered to an individual participant. The washout interval may be adjusted based on data emerging from previous cohorts/periods.
- Dose escalation to occur following review of PK data through at least 24 hours post-dose and safety and tolerability data through at least 48 hours post-dose of the current period. Cumulative safety and tolerability data from all previous periods will also be reviewed.
- It is anticipated that the effect of food (dose administration with a high fat breakfast) on PF-06954522 PK
  will be assessed in the last Period of Cohort 1. This will be assessed at a dose level (to be chosen based on
  emerging data) that has been previously administered fasted within the same cohort. However, the effect of
  food may be assessed during any of the study periods/cohorts if thought necessary to achieve study objectives.
- On-site follow-up visit to occur 7-10 days after administration of the final dose of study intervention. Followup contact may occur via telephone contact and must occur 28-35 days after administration of the final dose of study intervention.
- DER: dose escalation review; Pbo: placebo; TBD: to be determined.

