#### 3.1.1. Adverse Events

An AE is considered a TEAE if the event started during the effective duration of treatment. All events that start on or after the first dose of study intervention, but before the end of the study will be flagged as TEAEs. The algorithm will not consider any events that started prior to the first dose date.

Events that occur in a non-treatment period (eg, washout or follow-up) will be counted as treatment emergent and attributed to the most recent treatment taken.

A 3-tier approach for summarizing AEs will not be used due to the low number of participants planned to be recruited.

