# 6.1. Primary Endpoint(s)

#### 6.1.1. Adverse Events

AEs will be listed and summarized by treatment and overall by population and in accordance with sponsor reporting standards using the safety population defined in Section 4.

Incidence and severity of TEAE tables will additionally be produced ('All causality' and 'Treatment related,' separately) to summarize the total number of adverse events by preferred term, which will be reported by treatment and overall by population, in accordance with sponsor reporting standards using the safety analysis set defined in Section 4.

The AEs will be presented sorted in descending frequency based on the overall number of AEs (by preferred term or system order class as appropriate) across doses.

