#### 6.1.2. Clinical Safety Laboratory Data

Safety laboratory data will be listed and summarized by treatment and overall by population, in accordance with the sponsor reporting standards using the safety analysis set defined in Section 4. Baseline is as defined in Section 3.1.2.

Data collected at screening that are used for inclusion/exclusion criteria, will be considered source data, and will not be required to be reported, unless otherwise noted.

In summary and listing tables, laboratory abnormalities occurring pre-dose on Day -1 for each period starting with Period 2 (or a participant's individual second dosing Period, for any participant that starts the study after Period 1), will be attributed to the dose from the previous period (e.g., for Cohort 1, an occurrence pre-dose at Period 2 Day -1 will be attributed to the Period 1 dose). Any abnormality pre-dose in Period 1 or pre-dose at a participant's first dosing period would be reported as that participant's baseline measure for the period. Unplanned assessments will be included in summary abnormality tables and listings.

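### By-treatment AE tables count 28-35 days after a cohort's final dose (anticipated fed in Cohort 1) but only 7 to about 12 days after earlier doses, with no common-window table

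*SAP*

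**What the plan says.** SAP 3.1.1 treats every event that starts between the first dose and the end of the study as treatment emergent. Events in washout or follow-up "will be counted as treatment emergent and attributed to the most recent treatment taken". No maximum number of days since dosing is set.

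SAP 6.1.1 states that "AEs will be listed and summarized by treatment and overall by population". SAP 6 defines treatment here as dose, population and dietary allocation, so fed and fasted dosing at the same dose are separate columns. The SAP describes no fixed-window, exposure-adjusted or by-period AE table, and SAP 6.5.3 marks treatment exposure as not applicable.

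On timing:

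- Consecutive doses are at least 7 days apart, with no stated maximum (SAP 2.3, Protocol 4.1).
- After the last dose, SAP 2.3 provides: "On-site follow-up visit to occur 7-10 days after administration of the final dose of study intervention". A further contact follows at 28-35 days.
- Protocol 8.4.1 has AEs collected "through and including a minimum of 28 calendar days" after the last administration.
- The food effect is anticipated to be one that "will be assessed in the last Period of Cohort 1" (SAP 2.3), at a dose already given fasted in that cohort.
- Protocol 4.1 gives total participation as "approximately 13 weeks for Cohort 1, 12 weeks for optional Cohort 2 and 11 weeks for optional Cohort 3", whereas the synopsis says it "will be approximately 15 weeks for each participant".

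**The concern.** In a crossover with balanced sequences, a longer last window would be shared across treatments. Here doses ascend, so the treatment given in the final period is not balanced over periods. In Cohort 1 it is the fed dose, or the last Cohort 1 dose if no fed period is run. In Cohort 2 it is the last dose given.

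Three comparisons in the AE tables therefore set unequal observation times side by side:

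- fed versus fasted at the same dose
- the final dose versus earlier doses
- the last Cohort 2 dose versus pooled placebo (SAP 5.2 pools placebo over the escalation periods and excludes the fed period)

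Fed active versus fed placebo is matched, because both fall in the same period.

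SAP 3.1 makes AEs by dose and dietary allocation part of the primary endpoint, and Protocol 4.2 says the fed assessment is also meant to explore safety and tolerability. All-causality tables could show more background or late events under the fed or final dose simply because those columns cover more days.

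**Working it through.** **Step 1. Reproduce the plan's durations.** Inputs: screening up to 28 days, minimum spacing 7 days, last contact at up to 35 days (Protocol 4.1), and 5, 4 and 3 periods (Protocol 1.3). Total days = 28 + 7 x (periods - 1) + 35.

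- Cohort 1: 28 + 4 x 7 + 35 = 91 days = 13 weeks
- Cohort 2: 28 + 3 x 7 + 35 = 84 days = 12 weeks
- Cohort 3: 28 + 2 x 7 + 35 = 77 days = 11 weeks

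All three match Protocol 4.1, so its durations correspond to 7-day windows for the earlier periods.

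**Step 2. Window ratio at 7-day spacing.** 28/7 = 4 and 35/7 = 5. With about 8 active participants per Cohort 1 period (Protocol 9.5), a fasted dose has 8 x 7 = 56 participant-days. The fed dose has 8 x 28 = 224 to 8 x 35 = 280.

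**Step 3. Spacing implied by the synopsis's 15 weeks (105 days), Cohort 1.**

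- Contact at day 35: (105 - 28 - 35)/4 = 10.5 days; ratio 35/10.5 = 3.3
- Contact at day 28: (105 - 28 - 28)/4 = 12.25 days; ratio 28/12.25 = 2.3

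Over both scenarios, the final dose carries between 28/(4 x 12.25 + 28) = 36% and 35/(4 x 7 + 35) = 56% of a Cohort 1 completer's post-dose days, although it is one dose of five.

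**Step 4. Effect on AE counts with no drug effect.** The documents give no background AE rate. Assume a constant 0.01 per participant-day, range 0.005-0.02. P(at least one AE) = 1 - exp(-rate x days).

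| Window (days) | 0.005/day | 0.01/day | 0.02/day | Expected of 8 at 0.01/day |
|---|---|---|---|---|
| 7 | 3.4% | 6.8% | 13.1% | 0.5 |
| 10.5 | 5.1% | 10.0% | 18.9% | 0.8 |
| 12.25 | 5.9% | 11.5% | 21.7% | 0.9 |
| 28 | 13.1% | 24.4% | 42.9% | 2.0 |
| 35 | 16.1% | 29.5% | 50.3% | 2.4 |

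**Step 5. Last Cohort 2 dose versus pooled placebo.** Suppose both cohorts run at 7-day spacing, Cohort 1's last period is fed, and 2 participants receive placebo per period. Pooled placebo then has 4 x 2 = 8 dosing occasions from Cohort 1 and 4 x 2 = 8 from Cohort 2. Of these 16, the 2 in Cohort 2's final period have the long window.

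- (14 x 7 + 2 x 28)/16 = 9.6 days; ratio 28/9.6 = 2.9
- (14 x 7 + 2 x 35)/16 = 10.5 days; ratio 35/10.5 = 3.3

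**The case against.** The study is descriptive, with no hypothesis test, and SAP 3.1 defines AE assessment over the entire study. Charging late events to the most recent treatment loses nothing. Study day is counted within period (SAP 6), so a late event can be recognised in listings that show study day. Treatment-related tables are produced separately, and the sponsor reporting standards that SAP 6.1.1 cites are not available for review. The listed food-effect endpoints are PK only, and the fed period is only anticipated to come last. The constant-rate illustration probably overstates the contrast: participants are confined through at least Day 4 of each period, while after the on-site follow-up visit the only scheduled collection point is one contact, possibly by telephone.

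Several of these points limit the concern:

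- The Step 4 figures should be read as upper bounds for the assumed rates.
- The 12-day figure is derived from the synopsis and is not a limit set by the plan.
- A participant who stops early gives the long window to an earlier treatment.
- If Cohort 2 repeats an earlier dose, SAP 5.2 combines the data, which dilutes the Cohort 2 ratio.

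None of them removes the imbalance. Listings do not correct the by-treatment tables, and the SAP text specifies no table that does. AEs by dietary allocation belong to the primary endpoint whatever the food-effect objective says. A window chosen after the data are seen would also be weaker than one set in advance.

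**Conclusion.** The concern holds, as an inexpensive improvement to descriptive tables. Followed exactly, the attribution rule gives a cohort's final treatment a window 4-5 times as long at 7-day spacing, or 2.3-3.3 times as long in Cohort 1 if the 15-week duration applies. The window difference follows directly from the documents. Its effect on counts, roughly one to two extra participants of 8 at 0.01 per day, rests on an assumed rate and on equal ascertainment in and out of the unit. Early in-unit effects, treatment-related tables and escalation decisions (which use safety data through at least 48 hours post-dose) are little affected.

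**What to change.** In SAP 3.1.1 and 6.1.1, keep the planned most-recent-treatment table and footnote it with the days at risk per treatment. Add one by-treatment table of treatment-emergent events with onset from dosing to the earlier of the next dose or 10 days post-dose. Show later follow-up events in a separate column, and keep all events in the totals and listings.

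Ten days is suggested so that findings at the 7-10 day on-site visit still count for the final dose. This parallels SAP 6.1.2, where "laboratory abnormalities occurring pre-dose on Day -1 for each period starting with Period 2" are charged to the preceding dose.

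The cost is one table and one derived flag, with no data lost. At minimum spacing a difference of 10 versus 7 days remains: a ratio of 10/7 = 1.4, or 9.5% versus 6.8% at 0.01 per day. It disappears if doses are 10 or more days apart. A 7-day cap would equalise completed periods fully but would drop events first arising on days 8-10 after the final dose from the windowed column.

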# 3.1.2. Clinical Safety Laboratory Data

Safety laboratory tests will be performed as described in the protocol.

The investigator must review the laboratory report, document this review, and record any clinically significant changes occurring during the study in the AE section of the CRF. Clinically significant abnormal laboratory test findings are those that are not associated with the underlying disease, unless judged by the investigator to be more severe than expected for the participant's condition.

Baseline will be the last pre-dose measurement in each study period.

To determine if there are any clinically significant laboratory abnormalities, the hematological, clinical chemistry (serum) and urinalysis safety tests will be assessed against the criteria specified in the sponsor reporting standards. The assessment will take into account whether each participant's baseline test result is within or outside the laboratory reference range for the particular laboratory parameter.

#### 3.1.3. Vital Signs

Single supine blood pressure and pulse rate measurements will be taken at screening, follow-up visit and at early termination (if applicable). Triplicate supine measurements will be taken at all other times as detailed in the Schedule of Activities (SoA) in the protocol. The average of the triplicate measurements will be calculated prior to analyzing the data. Respiratory rate and temperature will be measured at each timepoint specified in the protocol.

Baseline for these measures will be defined as the average of the triplicates (if applicable) at last nominal pre-dose measurement time in each study period.

The following endpoints will be determined:

- Change from baseline (CFB) in systolic and diastolic BP, pulse rate, respiratory rate and temperature.
- The minimum and maximum post-dose systolic and diastolic BP, pulse rate, respiratory rate and temperature.

The maximum increase and decrease from baseline over all measurements taken postdose for systolic and diastolic BP, pulse rate, respiratory rate and temperature values

The maximum increase from baseline will be calculated by selecting the maximum change from baseline over the respective period, except in the case where a participant does not show an increase. In such an instance, the minimum decrease should be taken. Similarly, the maximum decrease from baseline will be determined by selecting the minimum value of the change from baseline. In cases where a participant does not show a decrease, the minimum increase should be taken.

## 3.1.4. Continuous Cardiac Monitoring

Continuous cardiac monitoring will be performed using telemetry as outlined in the protocol.

All abnormal rhythms will be recorded and reviewed by the study physician for the presence of rhythms of potential clinical concern. The time, duration, and description of the clinically significant event will be recorded in the CRF.

Events deemed of clinical concern will be recorded as AEs and will be summarized as part of the standard AE outputs.

## 3.1.5. Electrocardiograms

A single 12-lead ECG will be obtained on all participants at screening, follow-up visit and at early termination (if applicable). 12-lead ECGs will be recorded in triplicate at all other times as detailed in the SoA in the protocol. The average of the triplicate readings collected at each assessment time will be calculated for each ECG parameter. If one or two of the triplicates are missing, the non-missing values will be used for the average, and missing values will not be imputed.

If any of the 3 individual ECG tracings has a QTcF value >500 msec, but the mean of the triplicates is not >500 msec, the data from the participant's individual tracing will be described in a safety section of the CSR in order to place the >500- msec value in appropriate clinical context. However, values from individual tracings within triplicate measurements that are >500 msec will not be included in the categorical analysis unless the average from the triplicate measurements is also >500 msec.

The average of the triplicate ECG measurements over the 3 pre-dose measurement times (-1H, -0.5H, and pre-dose 0H; total of 9 ECG measurements) collected before morning dose administration on Day 1 will serve as each participant's baseline value in each study period.

ECG endpoints include heart rate, QT interval, PR interval and QTcF and QRS complex. If not supplied QTcF will be derived using Fridericia's heart rate correction formula [1]:

QTcF (msec) = QT (msec) / (RR)1/3 where RR (sec) = 60/HR (if RR not provided).

The following endpoints will be determined:

• Change from baseline in QT, QTcF, PR, QRS interval and heart rate

- The maximum post-dose QTcF, heart rate, PR and QRS interval
- The maximum increase from baseline over all measurements taken post-dose for QTcF, heart rate, PR and QRS values

The maximum increase from baseline will be calculated by selecting the maximum change from baseline over the respective period, except in the case where a participant does not show an increase. In such an instance, the minimum decrease should be taken.

